9.4.2 ANALYSIS OF THE PRIMARY ENDPOINT

9.4.2.1 NDURE FEASIBILITY STUDY

For the primary endpoint (NDURE Accrual Rate), we will calculate the proportion and frequency of eligible patients who accrue (overall, white, and African American). Given its pilot nature, the study is not designed to evaluate racial differences in accrual, although reasons for study decline will be collected, analyzed for each racial subgroup, and used to refine recruitment.

9.4.2.2 RCT OF NDURE VERSUS USUAL CARE

For the primary endpoint (delays starting PORT as defined in **Section 8.1, Endpoint and Other Non-Safety Assessments**), we will calculate the percentage of patients who start PORT > 6 weeks after surgery and corresponding 95% confidence interval (CI) for both arms and for white and AA subgroups within each arm in the efficacy analysis population. The rate of PORT delay will be compared between arms using a Mantel-Haenszel test of two proportions, with strata defined by race and location of radiation facility.

Every effort will be made to minimize missing data and lost-to-follow-up participants. Participants will complete assessments at baseline and post intervention using an iPad-based REDCap collection method. The program coordinator will attempt to contact patients at least three times using a variety of methods of communication (e.g. text message, phone call, email, mail, etc) to complete outcome measures. This method resulted in 100% instrument completion in prior studies conducted by our team.

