4.2 RCT OF NDURE VERSUS USUAL CARE

4.2.1 OVERALL DESIGN

We will conduct a single-site, non-blinded, parallel-group, RCT of NDURE versus usual care for the management of delays and racial disparities starting PORT in adults with surgically-managed, locally advanced HNSCC. The study is designed to test the following hypotheses: 1) NDURE will result in a lower rate of delayed PORT relative to usual care (primary objective) and 2) NDURE will result in a smaller difference in PORT delay between AA and whites relative to usual care (secondary objective). The statistical plan for this between-group design analyzes the superiority of NDURE relative to usual care, although our power analysis is calculated with $\alpha = 0.1$ and $1 - \beta = 0.8$ based on the desire to emphasize power over type I error at this early stage of development (single-site pilot RCT) to ensure follow-up on promising interventions.

Upon enrollment and completion of the baseline assessments, patients will be randomized 1:1 to NDURE or usual care using a permuted block randomization method, with randomly selected block sizes of 2 or 4. Randomization, which will occur at the individual patient level, will be stratified with a 1:1 allocation ratio with strata defined by race (white, AA) and location of radiation facility (MUSC, non-MUSC) because of the known association of these variables with PORT delay^{6,33}. Furthermore, to facilitate evaluation of PORT delay rates in racial subgroups, we will oversample AAs for a final sample size of 50 white and 25 AA patients in each arm (see details in **Section 9.4.6, Sub-Group Analyses**). Given the impossibility of delivering the NDURE intervention in a non-blinded fashion, allocation concealment will be non-blinded. The study statistician ([name]) will generate the randomization schema and

randomization list. The study coordinator will implement the randomization. Randomization errors will be handled as per the modified intention-to-treat (ITT) population for the efficacy analysis.

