9 STATISTICAL CONSIDERATIONS

9.1 STATISTICAL HYPOTHESES

- Primary Endpoint:

PORT Delay

We hypothesize that, compared with patients who receive usual care, patients who receive NDURE will have a decreased rate of PORT delay (initiation of PORT > 6 weeks after surgery). Alternatively, our null hypothesis is that there will be no difference in the rate of PORT delay between NDURE and usual care.

The preliminary efficacy analysis will be calculated for the primary endpoint over the 6 week time period from the date of definitive surgical resection of the primary tumor.

- Secondary Endpoints:

PORT Delay

We hypothesize that, compared with usual care, NDURE will result in a smaller difference in the rate of PORT delay (initiation of PORT > 6 weeks after surgery) between AA and white patients. Alternatively, our null hypothesis is that there will be no difference in the rate of PORT delay between AA and white patients between NDURE and usual care.

The preliminary efficacy analysis will be calculated for the primary endpoint over the 6 week time period from the date of definitive surgical resection of the primary tumor.

TTP

We hypothesize that, compared with patients who receive usual care, patients who receive NDURE will have a shorter median TTP (time, in days, between the date of definitive surgical resection to the initiation of PORT). Alternatively, our null hypothesis is that there will be no difference in median TTP between NDURE and usual care.

TTP

We hypothesize that, compared with usual care, NDURE will result in a smaller difference in the median TTP between AA and white patients. Alternatively, our null hypothesis is that there will be no difference in the median TTP between AA and white patients between NDURE and usual care.

NDURE Accrual

We hypothesize that at least 60% of eligible subjects for the NDURE study will accrue to the study. Alternatively, our null hypothesis is that less than 60% of eligible subjects for the NDURE study will accrue to the study.

The preliminary feasibility analysis will be calculated for the secondary endpoint using the first 25 patients eligible to accrue to the study, which is expected to occur over 4 months.

NDURE Completion

We hypothesize that at least 85% of subjects who enroll in the NDURE study (at least 13 of 15 subjects) will complete all 3 NDURE sessions. Alternatively, our null hypothesis is that less than 13 of the 15 subjects who enroll in the NDURE study will complete all 3 NDURE sessions.

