9.4.3.2 RCT OF NDURE VERSUS USUAL CARE

We will analyze the secondary endpoint of TTP as a continuous variable and estimate median time to PORT for each arm and for racial subgroups within each arm using Kaplan-Meier curves with Greenwood variance estimation to construct the corresponding 95% CIs. Hazard ratio comparing the two arms will be estimated using Cox proportional hazards regression controlling for the stratification variables. TTP will be compared between intervention arms using a stratified log-rank test on the modified ITT efficacy analysis population.

For the secondary endpoints of barrier reduction and unresolved barriers, we will calculate the proportion of unresolved barriers and the frequency of unresolved barriers (respectively) at the end of NDURE, consistent with prior PN studies⁵¹. We will use logistic regression to assess the relationship between unresolved barriers and the rate of PORT delay (primary endpoint), controlling for covariates listed in **Section 8.1**.

For other secondary endpoints, data will be summarized using frequency and percent for categorical variables and using mean, median, standard deviation, IQR and range for continuous variables. We will construct 95% CIs to provide a measure of uncertainty in estimated proportions and means. Comparisons between trial arms of other secondary endpoints will be performed using *t*-tests and chi-square tests, or Wilcoxon rank sum and Fisher's exact tests as appropriate. Pre- and post-intervention values of variables measuring the theoretical constructs underlying NDURE (i.e. care coordination, self-efficacy in cancer care, support, and knowledge) will be compared using Wilcoxon sign rank tests. Comparisons between arms of the change in scores will be conducted using Wilcoxon rank sum tests. All secondary endpoint

will be analyzed on the modified ITT efficacy analysis population. Missing data will be handled as described in **Section 9.4.2.2, RCT of NDURE Versus Usual Care**.

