9.4.6 SUB-GROUP ANALYSES

Planned sub-group analyses of the primary endpoint will occur based on age and sex to evaluate the impact of inclusion across the lifespan and sex as biologic variables. Historical data have not established an association between either age or sex with the primary endpoint⁶. Given the importance of race to the study objectives, analysis of the primary endpoint by race is evaluated as a secondary objective instead of planned subset analysis. Additional planned subset analyses will evaluate the impact of the NDURE intervention on the primary endpoint based on insurance status and fragmentation of care between the surgical facility and radiation facility, both of which have been described as risk factors for delayed PORT⁶. As such, both of these variables have the potential to confound the effect of the intervention were they to be imbalanced in a future RCT. As such, evaluating their impact on the primary endpoint in this study would allow for rational stratification in planned future RCTs.

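### The racial-disparity hypothesis has a stated null, but the plan pre-specifies no arm-by-race contrast, interval or test for PORT delay or for median time to PORT

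*Combined protocol and SAP*

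**What the plan says.** Section 4.2.1 lists the disparity question as the second of two hypotheses that the RCT is designed to test. Section 9.1 repeats it: compared with usual care, "NDURE will result in a smaller difference in the rate of PORT delay" between AA and white patients. The null there is that "there will be no difference in the rate of PORT delay between AA and white patients between NDURE and usual care". Section 9.1 states a parallel hypothesis and null for the AA-white difference in median TTP. In the section 3 table it is the first secondary objective of the RCT.

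On analysis, section 9.4.2.2 plans percentages with 95% CIs for each arm and "for white and AA subgroups within each arm". The delay rate is then "compared between arms using a Mantel-Haenszel test of two proportions, with strata defined by race and location of radiation facility". For TTP, section 9.4.3.2 plans medians by arm and "for racial subgroups within each arm using Kaplan-Meier curves", a Cox model adjusted for the stratification variables, and a stratified log-rank test of the arms.

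Section 4.2.1 sends the reader to section 9.4.6 for details of the racial subgroups. Section 9.4.6 replies that "analysis of the primary endpoint by race is evaluated as a secondary objective instead of planned subset analysis". Section 9.4.3.2, which covers the secondary endpoints, then contains no analysis of PORT delay by race.

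**The concern.** A claim that navigation narrows a disparity is a claim about how the AA-white gap differs between arms, which is an arm-by-race interaction on the scale of the gap. The plan names no such quantity. It fixes no scale, model, interval or significance level for it. Anyone following the plan exactly would report four rates and four medians and leave the reader to compare two gaps by eye, with no statement of how uncertain that comparison is. The scale and model would be chosen after the data are seen. Disparity is in the trial's title, and AA patients are oversampled so that racial subgroups can be evaluated, so this is a central aim.

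**Working it through.** **1. The plan's own figure.** Section 9.2.2 gives 83% power for 45% versus 25%, 75 per arm, two-sided alpha 0.10. The pooled SE is sqrt(2 × 0.35 × 0.65 / 75) = 0.0779. The unpooled SE is sqrt(0.45 × 0.55/75 + 0.25 × 0.75/75) = 0.0762. Power = Φ((0.20 − 1.645 × 0.0779)/0.0762) = 82.7%, so the figure reproduces. It concerns the arm comparison only. No power or precision is given for the disparity hypothesis.

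**2. Does the planned test respond to the gap?** The race-stratified Mantel-Haenszel test was simulated at alpha 0.10 (race strata only, without facility). The arm effect was held at 20 points on average and the usual-care gap at 12.6 points.

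| Gap under NDURE | Rejection rate |
|---|---|
| closed (0 points) | 83.4% |
| unchanged (12.6 points) | 83.5% |
| widened (25 points) | 84.0% |

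The result is essentially the same whether the disparity closes, persists or doubles. The stratified log-rank test and the Cox model without an interaction term share the limitation, since each yields one arm effect across the races.

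**3. Precision of the missing contrast.** Define D = (AA − white delay rate in usual care) − (AA − white delay rate in NDURE), with SE = sqrt(Σ p(1 − p)/n) over the four cells. Cell sizes of 50 white and 25 AA per arm come from section 4.2.1.

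The documents give no race-specific rates, so these are assumptions: usual care averages 45% over the 2:1 mix, and NDURE is 25% in both races, meaning the gap is fully closed. Section 2.2.2 says AA patients are 31% more likely to be delayed, after adjustment, without stating whether this is a risk ratio or an odds ratio.

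Read as a risk ratio: white rate = 0.45/(2/3 + 1.31/3) = 0.408, AA rate = 1.31 × 0.408 = 0.534, gap 12.6 points.

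SE = sqrt(0.408 × 0.592/50 + 0.534 × 0.466/25 + 0.25 × 0.75/50 + 0.25 × 0.75/25) = 0.161.

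Half-widths: 1.645 × 0.161 = 26.5 points (90%) and 1.96 × 0.161 = 31.6 points (95%).

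**4. Power to detect full closure**, as Φ(D/SE − z) + Φ(−D/SE − z):

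| Assumed usual-care gap | White / AA | SE | Alpha 0.10 | Alpha 0.05 |
|---|---|---|---|---|
| 6.7 points (31% as odds ratio) | 42.8% / 49.5% | 0.162 | 13% | 7% |
| 12.6 points (31% as risk ratio) | 40.8% / 53.4% | 0.161 | 20% | 12% |
| 20 points | 38.3% / 58.3% | 0.160 | 35% | 24% |
| 31 points | 34.7% / 65.7% | 0.158 | 63% | 50% |

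Simulation of the risk-ratio row gave 22% and 14%. The change in gap detectable with 80% power is (1.645 + 0.842) × 0.161 ≈ 40 points at alpha 0.10 and (1.96 + 0.842) × 0.161 ≈ 45 points at 0.05.

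**5. Which alpha?** Sections 4.2.1 and 9.2.2 use 0.10 for the design. Section 9.4.1 sets 0.05 and 95% CIs for inferential tests. Nothing says which governs this hypothesis.

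**The case against.** The best defence is that this is a secondary objective of a single-site pilot, framed as preliminary impact. The oversampling is justified by the wish to evaluate delay rates in racial subgroups, and section 9.4.2.2 reports exactly those rates. No go/no-go rule depends on the disparity result, and the primary comparison is untouched. All of that stands, and it excuses low power. It does not excuse a formal null with no analysis attached.

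It could also be said that the general clause in section 9.4.3.2 (t, chi-square, Wilcoxon or Fisher tests) covers the gap. It does not, because those tests compare arms on an endpoint and do not compare AA-white differences between arms.

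Two stronger readings are tempting. A reader might infer that the trial cannot answer its second hypothesis. The documents do not support that: race is used in the stratification or sampling (sections 4.2.1 and 6.3), all four cell rates will be reported, and the change in gap and its SE follow from them by arithmetic. What is missing is the pre-specification. A reader might also infer that the sponsor will declare success if the gap is significant under usual care but not under NDURE. The plan contains no AA-versus-white test within an arm, so an error rate for that procedure cannot be charged to it.

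**Conclusion.** The point holds as a gap between a stated hypothesis and the stated analyses. Followed exactly, the plan neither estimates nor tests the change in the racial gap, for PORT delay or for median TTP. This does not depend on any assumed rate.

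The size of the imprecision does rest on assumptions (45% overall in usual care, 25% in both races under NDURE, planned cell sizes achieved). The SE is stable at about 16 points across the scenarios. Power varies widely because the true gap is unknown, and is low if the gap is near the 31% the protocol cites. A non-significant contrast would therefore say little, and could not be read as evidence that disparity is unchanged.

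**What to change.** In section 9.4.3.2:

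- **PORT delay.** Name the contrast D defined above, on the risk-difference scale, in the modified ITT population. Estimate it from one named model, for example a linear-probability model with robust SEs containing arm, race, arm × race and facility. With NDURE and AA each coded 1, D is minus the interaction coefficient.
- **TTP.** Report the same difference of differences in Kaplan-Meier medians with a bootstrap CI. A Cox arm × race term can be supportive only: it estimates a ratio of hazard ratios, while section 9.1 hypothesises a difference in medians.
- **Level.** Give one CI level for both, and settle the 0.10 versus 0.05 conflict between sections 4.2.1 and 9.2.2 on one side and 9.4.1 on the other.
- **Interpretation.** Label both contrasts as estimation. State that no claim of reduced or unchanged disparity will rest on separate subgroup rates or on a non-significant contrast.
- **Cross-reference.** Point sections 4.2.1 and 9.4.6 to this text.

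The cost is SAP wording and one extra model per endpoint, with no new data or patients. The downside is that a headline aim becomes visibly imprecise.

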9.4.3 ANALYSIS OF THE SECONDARY ENDPOINTS

9.4.3.1 NDURE FEASIBILITY STUDY

NDURE completion rate will be analyzed as 1) the percentage of enrolled patients who attend all three NDURE sessions and 2) the proportion of three NDURE sessions that are completed. For navigator caseload, we will consider the frequency of simultaneous cases navigated. Navigator time allocation for direct and indirect time, as well as patient-report measures of satisfaction with navigation will be summarized as described above for continuous data. Study questionnaire completion rate will be calculated as the proportion of pre- and post-intervention questionnaires (n=5 each) completed. Qualitative data will be analyzed using established team codebooks and focus on the content, format, delivery, and timing of NDURE. Qualitative analysis of semi-structured interviews with patients and providers following the pilot will be analyzed using established codebooks from the study team for evaluating the feasibility and acceptability of clinic-based HNSCC interventions with a focus on the content, format, delivery, and timing of NDURE.

9.4.3.2 RCT OF NDURE VERSUS USUAL CARE

We will analyze the secondary endpoint of TTP as a continuous variable and estimate median time to PORT for each arm and for racial subgroups within each arm using Kaplan-Meier curves with Greenwood variance estimation to construct the corresponding 95% CIs. Hazard ratio comparing the two arms will be estimated using Cox proportional hazards regression controlling for the stratification variables. TTP will be compared between intervention arms using a stratified log-rank test on the modified ITT efficacy analysis population.

For the secondary endpoints of barrier reduction and unresolved barriers, we will calculate the proportion of unresolved barriers and the frequency of unresolved barriers (respectively) at the end of NDURE, consistent with prior PN studies⁵¹. We will use logistic regression to assess the relationship between unresolved barriers and the rate of PORT delay (primary endpoint), controlling for covariates listed in **Section 8.1**.

For other secondary endpoints, data will be summarized using frequency and percent for categorical variables and using mean, median, standard deviation, IQR and range for continuous variables. We will construct 95% CIs to provide a measure of uncertainty in estimated proportions and means. Comparisons between trial arms of other secondary endpoints will be performed using *t*-tests and chi-square tests, or Wilcoxon rank sum and Fisher's exact tests as appropriate. Pre- and post-intervention values of variables measuring the theoretical constructs underlying NDURE (i.e. care coordination, self-efficacy in cancer care, support, and knowledge) will be compared using Wilcoxon sign rank tests. Comparisons between arms of the change in scores will be conducted using Wilcoxon rank sum tests. All secondary endpoint

will be analyzed on the modified ITT efficacy analysis population. Missing data will be handled as described in **Section 9.4.2.2, RCT of NDURE Versus Usual Care**.

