1.3 SCHEDULE OF ACTIVITIES

Table 1. Schedule of Activities for NDURE and Usual Care and Follow-up

	Pre-screening	Visit 1	Visit 2 (Pre-Op)	Visit 3 (Pre-Discharge)	Visit 4 (Post-Discharge)	Visit 5 (Start of PORT)
Informed Consent						
Electronic Medical Record (EMR) Review Eligibility	X					
Informed Consent		X				
Study Procedures						
Randomization		X				
Demographics		X				
Clinical and Oncologic History		X			X	X
PORT Delay Nomogram		X				
Cultural Factor Survey		X				
Monitoring						
AE/SAE Assessment			X	X	X	X
Intervention Administration						
NDURE or UC			X	X	X	
Efficacy Evaluation						
PORT Delay						X
Feasibility						
NDURE Accrual	X					
NDURE Completion						X
Navigator Caseload		<----->				
Navigator Time Allocation		<----->				
Acceptability						
Satisfaction with the Interpersonal Relationship with the Navigator Scale						X
Satisfaction with Logistical Aspects of Navigation Scale						X
Program Evaluation						X
Cancer Care Delivery Processes						
Timely Care Processes		<----->				
Health Behavior Constructs						
Barrier Reduction				X	X	X
Unresolved Barriers			X	X	X	X
Care Transition Measure-15				X	X	

Interpersonal Support Evaluation List-12		X				X
Perceived Susceptibility Questionnaire		X		X	X	
Illness Perception Questionnaire-Revise Consequences Subscale		X		X	X	
Perceived Barriers Questionnaire		X		X	X	X
Communication & Attitudinal Self-Efficacy Scale-Cancer		X				X
Navigator Barrier Log		X		X	X	X

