6 STUDY INTERVENTION

6.1 STUDY INTERVENTION ADMINISTRATION

6.1.1 STUDY INTERVENTION DESCRIPTION

6.1.1.1 NDURE

NDURE is a theory-based, multi-level PN intervention consisting of three sessions of manualized PN with multiple intervention components that target system- (care coordination), interpersonal- (social support), and individual- (HBM; perceived susceptibility, severity, barriers, self-efficacy) level health behavior theoretical constructs to reduce barriers to care, increase HNSCC care delivery, and improve clinical outcomes (timely, equitable PORT). The NDURE intervention components and targeted theoretical constructs are outlined in **Table 2**. NDURE will be delivered from surgical consultation to PORT initiation (~3 months). The three NDURE navigation sessions, which are expected to take 30-60 minutes each, will coincide with the presurgical consult, hospital discharge, and 1st postoperative clinic visit, time points chosen to facilitate case identification and coordination across key care transitions. The preferred method for delivering NDURE is face to face. However, due to changes in healthcare delivery necessitated by COVID-19 pandemic, it is permissible for the NDURE navigator to use a telemedicine videoconferencing platform for NDURE sessions 1 or 3 (study visit 2 or 4). Contact beyond the three prescribed sessions will occur with a frequency and modality (e.g. text message, email, etc.) dictated by patient and navigator need. During the first session, the navigator will 1) elicit barriers and facilitators to timely PORT from the patient, caregiver, and provider, 2) develop the personalized barrier reduction plan (BRP), review it with the patient, caregiver, and provider, and 3) implement the BRP. At the two subsequent sessions, the navigator will review and update the BRP in an iterative, dynamic fashion, identifying new barriers and systematically tracking resolution of prior barriers until the start of PORT. The Navigator Manual

Table 2. NDURE Intervention Components

Component	Description	Theoretical Target
Clinical Tool		

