8 STUDY ASSESSMENTS AND PROCEDURES

8.1 ENDPOINT AND OTHER NON-SAFETY ASSESSMENT

Feasibility

NDURE Accrual Rate is defined as the proportion of eligible patients who enroll in NDURE

NDURE Completion Rate is defined as the proportion of enrolled patients who complete the baseline assessment, at least two NDURE intervention sessions, and the final follow-up assessment

Navigation Session Completion Rate is the proportion of NDURE navigation sessions completed by each individual

Navigator Caseload is the number of simultaneous cases (on-trial participants) being navigated by the NDURE navigator

Navigator Time Allocation (Direct) is the time (in minutes), that the NDURE navigator spends directly interacting with the patient to identify and address barriers to timely, equitable PORT

Navigator Time Allocation (Indirect) is the time (in minutes), that the navigator spends generating and enacting each Barrier Reduction Plan that is not directly interacting with the patient

Questionnaire Completion Rate is the proportion of pre- and post-treatment questionnaires completed by enrolled patients

Acceptability

Satisfaction with the Interpersonal Relationship with the Navigator Scale Score is defined as the total score of this 9-item measure of the satisfaction of the interpersonal relationship with the patient navigator. This reliable and validated measure^{30,31} has been widely used in prior studies of PN. The total score of the measure ranges from 9 (minimum) to 45 (maximum); higher scores represent a better outcome (greater satisfaction with the interpersonal relationship with the navigator).

Satisfaction with Logistical Aspects of Navigation Scale Score is defined as the total score of the 26-item measure of the satisfaction of the logistical aspects of PN. This reliable and validated measure³² has been widely used in prior studies of PN. The total score of the measure ranges from 0 (minimum) to 78 (maximum); higher scores represent a better outcome (greater satisfaction with the logistical aspects of navigation).

Clinical Outcomes

PORT Delay is defined as the initiation of PORT more than 6 weeks (42 calendar days) from the date of the definitive surgical resection. In situations in which the surgical management of the primary tumor and

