the neck are staged (i.e. occur on two different calendar days), the date of the definitive surgery for the primary tumor will be used. In situations in which an additional surgical resection is required (e.g. re-resection of positive margins to clear residual disease), the date of the earlier (i.e. attempted definitive) surgical procedure will be used to determine the date of definitive surgical resection.

Time-to-PORT (TTP) is defined as the time, in days, between the date of definitive surgical resection to the initiation of PORT. All of the criteria used to adjudicate the date of the definitive surgical procedure described for the primary outcome measure will be applied to this measure.

Barriers to Care

Rate of barrier resolution is defined as the proportion of confirmed barriers (as determined by the navigator log) that are resolved during the NDURE intervention.

Unresolved barriers are the number of confirmed barriers (as determined by the navigator log) that are not resolved during the NDURE intervention.

Cancer Care Delivery Processes

Pre-Surgical Radiation Consultation is defined as the attendance by the patient at a consultation with a radiation oncologist (at MUSC or elsewhere) prior to surgery to discuss RT in the definitive or adjuvant setting

Pre-Radiation Therapy Dental Extractions is defined as the extraction of teeth prior to discharge from the index hospitalization for the definitive surgical procedure. Patients who are edentulous are not evaluable for this measure.

Surgery to Pathology Report <= 7 days is defined as the production of the pathology report from the definitive surgical procedure within the EMR within 7 calendar days of the definitive surgical procedure. Addenda to the pathology report at the request of the HNSCC team (e.g. tumor p16 status) are not counted in this measure.

Surgery to PORT Referral <= 10 days is defined as the placement of a referral for PORT, at MUSC or elsewhere, within 10 calendar days of the definitive surgical procedure.

RT Referral to Consult <= 10 days is defined as the evaluation of the patient at a postoperative consultation with a radiation oncologist within 10 calendar days of the referral being placed (or postoperative appointment being scheduled in cases in which care has been established and the return visit is no longer a consultation). The consultation may occur in the clinic or the hospital depending upon clinical circumstances.

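### The unresolved-barrier count used to model PORT delay is taken at PORT start, at or after the point that settles delay, so its association with delay is biased in an unpredictable direction

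*Combined protocol and SAP*

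**What the plan says.** Three parts of the plan bear on this.

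- **The exposure.** Section 8.1 defines it: "Unresolved barriers are the number of confirmed barriers (as determined by the navigator log) that are not resolved during the NDURE intervention". Section 9.4.3.2 fixes when it is read: "we will calculate the proportion of unresolved barriers and the frequency of unresolved barriers (respectively) at the end of NDURE".
- **When NDURE ends.** Sections 1.1, 4.2.1 and 6.1.1.1 have the intervention running from the surgical consultation to PORT initiation, about three months. Section 6.1.1.1 has the navigator "identifying new barriers and systematically tracking resolution of prior barriers until the start of PORT". In the Section 1.3 schedule, unresolved barriers are assessed at Visits 2, 3, 4 and 5, and Visit 5 is the start of PORT.
- **The outcome and the model.** Section 8.1: "PORT Delay is defined as the initiation of PORT more than 6 weeks (42 calendar days) from the date of the definitive surgical resection". Section 9.4.3.2 makes delay the dependent variable and unresolved barriers the predictor, with adjustment for the Section 8.1 covariates. It names no earlier count, landmark day or time-varying form.

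**The concern.** A predictor of delay should be read before delay is decided, over a period that does not depend on the answer. Here neither condition is met. A patient who starts PORT on day 70 has had 28 more days to close barriers than one who starts on day 42, simply because the first patient was late. Adjustment for baseline covariates cannot remove this, because the length of the window is the outcome in another form.

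This is the only specified analysis that links barriers to the primary endpoint. Reducing barriers is the stated mechanism of NDURE, and Section 4.2.1 gives refinement of the intervention as a purpose of the pilot. A coefficient with the wrong sign or size would be poor evidence for that work.

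**Working it through.** **The plan's own figures.** The documents give no figure for the barrier regression, so there is nothing to reproduce for this analysis. The headline power in Section 9.2.2 (75 per arm, 45% against 25%, two-sided alpha 0.1) recomputes to 82.7% against the stated 83%. It does not depend on the barrier analysis.

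**Timing, from the documents alone.**

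1. The count is read at PORT start, on day *t* after surgery.
2. Delay means *t* > 42.
3. Delayed patients have *t* of 43 or more, so their count is read after their status is fixed. On-time patients have *t* of 42 or less, so their count is read at the event that fixes it.
4. In both groups the post-surgical time for resolving barriers is *t*.

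**Why this biases the result even with no true effect.** Assume that barriers resolve exponentially with mean 30 days after surgery and have no influence on PORT. The chance that a barrier is still open at PORT start is exp(−*t*/30).

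- Start on day 42: exp(−1.40) = 0.247, so 3 barriers leave 3 × 0.247 = 0.74 open.
- Start on day 70: exp(−2.33) = 0.097, so 3 barriers leave 3 × 0.097 = 0.29 open.

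The later starter shows fewer open barriers although barriers did nothing.

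**Simulation A (every input is an assumption).** 100,000 patients per scenario; Poisson mean 3 barriers; mean resolution 30 days; between-patient spread in resolution speed with log SD 0, 0.5 or 1. From day 21 the daily chance of starting PORT is *h*·exp(−*b*·open barriers), with *b* = 0, 0.2, 0.5, 1, 2. Simulated delay is 35% to 42%. The PORT-start count is capped at day 90. Odds ratios (OR) for delay are per open barrier, in order of the three spreads.

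| Effect of an open barrier | Count at day 14 | Count at PORT start |
|---|---|---|
| None (*b* = 0) | 1.01, 0.99, 1.00 | 0.38, 0.51, 0.69 |
| Weak (0.2) | 1.19, 1.21, 1.24 | 0.49, 0.66, 0.90 |
| Moderate (0.5) | 1.49, 1.55, 1.65 | 0.66, 0.91, 1.27 |
| Strong (1) | 2.05, 2.25, 2.57 | 1.01, 1.48, 2.23 |
| Very strong (2) | 2.70, 3.06, 3.74 | 1.72, 2.73, 4.75 |

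Of the 12 scenarios with a real effect, the PORT-start OR is below 1 in five, about 1 in one, above 1 but weakened in five, and inflated in one.

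**Simulation B (a different assumed mechanism).** 200,000 patients per scenario; Poisson mean 2 barriers; mean resolution 25 days. PORT starts at the later of a readiness date (mean 36, SD 5 days) and 10 days after the last blocking barrier clears.

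| Share of barriers that block PORT | Day-14 OR | PORT-start OR |
|---|---|---|
| 0% | 1.00 | about 0.67 |
| 25% | 1.64 | 0.50 |
| 50% | 2.18 | 0.45 |
| 75% | 2.97 | 0.42 |
| 100% | 4.23 | not estimable: every count is zero |

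**Simulation B with some barriers that never resolve but slow PORT.** At 25%, 50% and 75% blocking:

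- 10% never resolve, 5 days' delay each: PORT-start OR about 1.30, 1.28, 1.51.
- 20% never resolve, 5 days each: 1.85, 1.83, 2.06 (day 14: 2.00, 2.40, 2.99).
- 20% never resolve, 10 days each: 3.27, 3.67, 4.78 (day 14: 2.51, 3.13, 4.05).

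In both models the day-14 count gives an OR of about 1 when there is no effect, and the PORT-start count does not. The direction of the error when there is an effect depends on the resolution pattern.

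**The case against.** **The strongest reading fails.** A reader might infer that the planned association must vanish or change sign, because a barrier that blocks PORT cannot still be open on the day PORT starts. The documents do not support that. They never define barriers as absolute blocks. Section 2.1 lists travel distance, finances, support and knowledge, which can slow PORT and still be present on its first day. Once some barriers never resolve, the OR stays above 1 and can exceed the early one. Reversal is possible but not established.

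**Nor is the count taken after the outcome in everyone.** That holds for delayed patients. In on-time patients the two coincide.

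**The end of NDURE can be read another way.** Section 6.1.2.1 defines the full dose as three sessions, and the Section 1.3 schedule marks intervention delivery only at Visits 2 to 4. On that reading the count would fall at Visit 4 and most of the problem would go. The explicit statements about duration and about barrier tracking up to PORT favour the later date. The ambiguity stands, and is itself a reason to define the term.

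**The stakes are limited.** The plan claims only to assess a relationship, in a secondary analysis of a pilot. Qualitative interviews also inform refinement of NDURE. Section 9.4.3.2 says the summaries follow earlier navigation studies, which cannot be checked here. That supports keeping them as descriptive results, but does not answer the timing problem in the regression.

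**Conclusion.** The timing defect holds and follows from the plan's text, on the reading that NDURE ends at PORT initiation. The regression uses a count read at or after the point when delay is determined, over a window equal to time-to-PORT, so its coefficient cannot be read as evidence on whether unresolved barriers lead to delay.

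The size is uncertain. With no true effect, the assumed models give a spurious OR of 0.38 to 0.69. With a true effect, results run from 0.42 to values above the day-14 OR. All of these rest on assumed barrier numbers, resolution times and PORT-start mechanisms, and on day 14 as a stand-in for Visit 4, which the documents do not tie to a fixed day.

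A reader might also infer that the main result is at risk. It is not: the stratified comparison of delay between randomised arms does not use barrier counts. Severity is minor to moderate.

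**What to change.** In Section 9.4.3.2:

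1. Define the end of NDURE as either PORT initiation or the third session, and reconcile this with Sections 1.3, 6.1.1.1 and 6.1.2.1.
2. In the logistic regression, use as the predictor the number of unresolved barriers at Visit 4, restricted to patients who at that visit have not started PORT and are still within 42 days of surgery.
3. Keep the end-of-NDURE resolution rate and unresolved count as descriptive summaries only.

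This takes a few sentences and no new data, since the Section 1.3 schedule already collects unresolved barriers at Visit 4. The cost is that barriers first appearing after Visit 4, including some around radiation referral and consultation, drop out of the model, as do any patients excluded by the restriction. Because Visit 4 has no fixed day, its timing after surgery should be reported with the result.
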